assessment to inform further modifications to the intervention components. Participants in Aim 1 will be patients of the outpatient clinics (OPC) or health care providers who work there. Patients who use tobacco will be asked to participate in individual interviews (n=24). We will conduct key informant interviews with health care providers from 3 OPCs (n=28) to adapt the intervention to the OPC clinical context. We will then conduct a pilot test of ARM 1 and 3 in one OPC with 16 patients. The recruitment and enrollment process will be the same as described for Aim 2. For Aim 2 we will conduct a three-arm randomized controlled trial (RCT) to compare the effectiveness of three interventions aimed at increasing tobacco cessation rates among people living with HIV/AIDS (PLWH). Patients (n=672) will be recruited and enrolled from the 13 OPCs. All enrolled patients will complete a baseline survey in person. This survey will be administered once eligibility is established and consent is obtained. The consent and survey will last 30 minutes. Follow up surveys will occur at 3- and 6-months after enrollment. Follow up surveys will be conducted by telephone. At 6-months follow up, patients who report smoking abstinence will be asked to come in person to the OPC and will complete a carbon monoxide test to validate self-report. We will conduct baseline and 12-month surveys with all health care providers in the study sites in person (n=98). For Aim 3 we will conduct 12-month post intervention interviews and an 18-month survey to assess factors associated with implementation effectiveness and potential for sustainability. For Aim 4 we will enroll 75 more patients who are non-smokers for a total of (n=747) patients and assess the relationship between food insecurity and tobacco use among PLWH (75 smokers and 75 non-smokers), which includes administering the Household Food Insecurity Access Scale (HFIAS) survey to patients at baseline and 6-months.

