3. OBJECTIVES. The objectives of the main study are 1) to conduct a formative assessment to guide adaptations of the current intervention components to optimize implementation of tobacco dependence treatment, 2) to conduct a 3-arm randomized controlled trial (RCT) that compares the effectiveness of three multi-component interventions that are embedded in HIV OPCs, and 3) to assess barriers and facilitators to implementation and potential for sustaining gains. (See schematic above). The objectives of the supplement are 1) to estimate the difference in household food insecurity among PLWH who smoke compared with PLWH who are non-smokers at baseline. 2) to examine mechanisms linking smoking and household food insecurity among PLWH at baseline and 6-months follow-up, and 3) to assess the impact of a reduction in tobacco use and tobacco cessation on measures of food Insecurity at 6-month follow-up.

4. STUDY DESIGN and ENDPOINTS

4.1 DESCRIPTION OF STUDY DESIGN. This is a phase 3 pragmatic comparative effectiveness study. **AIM 1:** We will collect pretrial data using individual interviews with tobacco users to inform further tailoring of the intervention for HIV+ smokers and individual interviews (n=28) with health care providers in three OPCs. We will then conduct a pilot test of ARM 1 and 3 in one OPC with 16 patients. **AIM 2:** We will then conduct a 3-arm RCT to compare the effectiveness of three multi component interventions: 1) Ask, Advise, Assist (AAA) + Refer to the national smokers' Quitline); 2) AAA+Counseling (Counsel) which adds referral to an onsite health worker for 6-sessions of cessation counseling tailored to PLWH; and 3) Addition of 6-weeks of nicotine gum (AAA+Counsel+N). Only ARM 3 participants will receive NRT. ARM 2 and 3 will receive two text messages daily for 8 weeks and then 1 per day for 4 weeks to reinforce the counseling protocol. A total of 747 participants will be recruited in 13 outpatient HIV clinics (OPCs) in Hanoi and randomized into one of the three arms (48 smokers per site, 16 per arm; about 5 non-smokers per site). The primary outcome for smokers is 6-months biochemically validated smoking abstinence. We will conduct baseline in person surveys with all providers (n=98).

AIM 3: We will conduct 12-month post intervention interviews and 18-month surveys with healthcare providers and other key informants to assess factors associated with implementation effectiveness and potential for sustainability.

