AIM 4: When comparing smokers and non-smokers at baseline on the HFIAS, power is 80% to detect a standardized mean difference of $d=0.46$ (about half a standard deviation, a difference of 3 HFIAS points assuming a standard deviation of 6) given the proposed sample size of $n= 150$ (75 smokers and 75 non-smokers). When estimating the relation between income and HFIAS, power is 80% to detect a squared multiple correlation of $R^2=.05$ given the proposed sample size of $n=150$. When estimating the impact of smoking cessation on HFIAS at the 6-month follow-up, power is 80% to detect a standardized mean difference of $d=0.89$ (about nine tenths of a standard deviation, a difference of 6 HFIAS points) given the proposed sample size of $n=75$ smokers at baseline and assuming at least 16% of smokers ($n=12$) achieve cessation.

9.2 STATISTICAL HYPOTHESIS. The primary hypothesis is that more intensive counseling delivered by a trained nurse (ARM 2) will be more effective than provider brief counseling plus Quitline counseling (ARM 1) in increasing smoking abstinence. We further hypothesize that adding nicotine replacement therapy to the more intensive counseling will increase cessation rates more than the intensive counseling alone (ARM 3).

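### Aim 4 measures HFIAS at baseline and 6 months, but nothing in the plan brings the baseline value into the estimate of the impact of quitting, although quitters are self-selected.

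*Combined protocol and SAP*

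**What the plan says.** Supplement objective 3, in section 3, is "to assess the impact of a reduction in tobacco use and tobacco cessation on measures of food Insecurity at 6-month follow-up". The Schematic of Design describes Aim 4 as including "administering the Household Food Insecurity Access Scale (HFIAS) survey to patients at baseline and 6-months", and section 4.1 AIM 4 gives the same two time points. Each smoker should therefore have a baseline value and a 6-month value.

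The AIM 4 paragraph of section 9.1 consists of three power statements. The one for cessation reads "When estimating the impact of smoking cessation on HFIAS at the 6-month follow-up, power is 80% to detect a standardized mean difference of" 0.89, "given the proposed sample size of $n=75$ smokers at baseline and assuming at least 16% of smokers ($n=12$) achieve cessation". No model, covariate list or use of baseline HFIAS follows.

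Two other places bear on the model:

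- **Protocol Summary, Statistical Analysis.** Food insecurity outcomes are to be analysed by conditional logistic regression or by another fixed effects regression suited to the outcome. The fixed effects approach is justified there by the modest number of clinics, and clinic is the stratification variable. No covariates are listed.
- **Section 9.1 AIM 2.** Patient characteristics, with sex, substance use and health as examples, are to be covariates in all analyses. Baseline HFIAS is not among the examples.

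**The concern.** The objective is worded causally, but quitting is not randomised within this comparison. Smokers who quit may already have had better or worse food security than those who did not. If the model omits baseline HFIAS, part of that starting difference appears at 6 months and is read as an impact of quitting. The outcome's own baseline value is also likely to be a strong predictor of the 6-month value. Omitting it leaves more residual variance than necessary, in a comparison that expects only 12 quitters.

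Leaving the model open also means that the choice among unadjusted, change-score and baseline-adjusted estimates could be made after the data are seen.

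**Working it through.** **Inputs from the documents.** 75 smokers, 16% quitting, so 12 v 63; detectable d = 0.89 at 80% power; 13 clinics. The SD of 6 comes from the baseline comparison ("a difference of 3 HFIAS points assuming a standard deviation of 6").

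**Assumptions.** Two-sided alpha of 0.05, which the AIM 4 paragraph does not state; the correlation r between baseline and 6-month HFIAS, taken as 0.3, 0.5 and 0.7; the starting gap, taken as 2 or 3 points; and no HFIAS variance explained by site.

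**1. Reproduce the plan's figure.** For an unadjusted two-sample t test the noncentrality is d × √S, with S = 12 × 63 / 75 = 10.08 and 73 df. At d = 0.89 power is 79.6% (80.7% by the normal approximation). The d giving exactly 80% is 0.894, or 0.894 × 6 = 5.4 points. One-sided 0.05 gives 87.6%, which does not match. The power basis therefore credits no baseline information. (The plan equates 0.89 SD with 6 points; at SD 6 it is 0.89 × 6 = 5.3.)

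**2. Baseline covariate, no site terms.** The residual SD becomes SD × √(1 − r²), with 72 df.

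| r | Detectable d | Points at SD 6 |
|---|---|---|
| none | 0.89 | 5.4 |
| 0.3 | 0.85 | 5.1 |
| 0.5 | 0.77 | 4.6 |
| 0.7 | 0.64 | 3.8 |

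**3. The same with the planned site effects.** With 12 quitters spread at random over 13 sites, the expected within-site value of S is 10.08 × (75 − 13)/(75 − 1) = 8.45. Residual df are 75 − 14 = 61 without baseline and 60 with it.

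| Model | Detectable d | Points at SD 6 |
|---|---|---|
| Site only | 0.98 | 5.9 |
| Site + baseline, r = 0.3 | 0.93 | 5.6 |
| Site + baseline, r = 0.5 | 0.85 | 5.1 |
| Site + baseline, r = 0.7 | 0.70 | 4.2 |

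This table applies to the regression in the Protocol Summary. Steps 2 and 3 ignore a small loss because quitting and baseline HFIAS would be correlated. For a 2-point gap, 0.16 × 0.84 × (2/6)² = 0.015, or about 1.5% of the information.

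**4. Starting gap carried into a 6-month-only contrast.** With no true effect, and a gap that regresses toward the mean, the expected 6-month difference is gap × r. The rejection rate comes from the test in step 1 with SD 6.

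| Gap (points) | r | Carried over (points) | Rejection of a true null |
|---|---|---|---|
| 2 | 0.3 | 0.6 | 6% |
| 2 | 0.5 | 1.0 | 8% |
| 2 | 0.7 | 1.4 | 11% |
| 3 | 0.3 | 0.9 | 8% |
| 3 | 0.5 | 1.5 | 12% |
| 3 | 0.7 | 2.1 | 20% |

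**5. Which sample?** Section 4.1 AIM 4 collects food insecurity data from 672 smokers. At 16% quitting that is 108 v 564, and the unadjusted detectable d is 0.29 (1.8 points). The larger sample does not remove the carried-over gap and makes it easier to declare significant: a 2-point gap rejects a true null 35% of the time at r = 0.5 and 60% at r = 0.7.

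**The case against.** The strongest reply is that a power statement is not an analysis plan. A reader might infer that Aim 4 will judge cessation from the 6-month difference alone. The documents do not say so: the AIM 4 paragraph names no model, the Protocol Summary foresees a regression, and the covariate sentence under AIM 2 speaks of all analyses with an open list. Nor does d = 0.89 identify the method, since a change-score analysis at r = 0.5 has the same detectable d. Leaving an unknown r out of a power calculation is common and conservative. This stands, and it limits the point to an omission. It does not fill the omission, because the fixed effect in the Protocol Summary is site and the covariate examples do not include the outcome's baseline value.

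A reader might also infer that the whole starting difference would be counted as an effect. Under the model used here only about r times the gap carries over, and the gap, its direction and r are all assumed.

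A further objection is that a baseline-plus-site model at r = 0.3 (0.93) does worse than the plan's 0.89. The arithmetic is right but the comparison is not like for like. Site effects are already planned, so the reference is 0.98.

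Finally, baseline adjustment is no cure. If quitters differ by a stable 2 points, it leaves 2 × (1 − r), or 0.6 to 1.0 points at r = 0.7 to 0.5. Income and smoking intensity could still confound. This stands and is why the result should be called an adjusted association.

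**Conclusion.** The point holds as an omission: baseline HFIAS is collected but not brought into the estimate of the impact of cessation. Without it, an assumed 2-point starting gap would put a spurious 1.0 to 1.4 points into the estimate at r of 0.5 to 0.7, with 8% to 11% false rejection; at r = 0.3 the effect is slight. Within the planned site regression, adding baseline lowers the detectable difference by about 5%, 13% or 29% at r of 0.3, 0.5 or 0.7 (0.93, 0.85 or 0.70 against 0.98).

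These sizes rest on the 12 v 63 split, SD 6, two-sided 0.05, no site variance, and values of r and the gap that the documents do not give. The conflict between 75 and 672 smokers affects precision more than baseline adjustment does. The matter concerns a supplement objective; the primary abstinence endpoint and the randomised arm comparisons are not affected. The change is worth making because it uses data already planned.

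**What to change.** In section 9.1 AIM 4, state that 6-month HFIAS is regressed on 6-month cessation, and in a separate model on reduction in tobacco use, with baseline HFIAS as a covariate, within the site fixed effects regression of the Protocol Summary. State that the coefficient is reported as an adjusted association, since other confounding such as income remains. A change score is a weaker substitute for precision: without site terms its detectable d is 1.06 at r = 0.3, and it beats the unadjusted contrast only when r exceeds 0.5.

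In the same edit, reconcile the 75 smokers of section 9.1 with the 672 of section 4.1 AIM 4, and restate the power for the sample and model chosen.

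The cost is one or two sentences and a revised power line, with no new data. Patients without a baseline HFIAS would drop out of the model, but the baseline survey is completed at enrolment, so few should be lost.

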Participant Duration	Patients and providers will be enrolled for 2 years
Duration of IP administration	Nicotine gum (for those randomized to Arm 3 in the RCT) will be given for 6 weeks.
Population	We are recruiting tobacco users who are patients at one of the 13 participating OPCs. All patients are Vietnamese. We will recruit women and men. For the research supplement (AIM 4) we will recruit non-smokers from the 13 OPCs.
Study Sites	13 HIV outpatient clinics in Hanoi
Number of participants	941 (includes providers and patient participants)
Description of Study Agent/Procedure	The intervention being tested in the RCT is behavioral only in ARM 1 and 2 and in ARM 3 patients will also receive nicotine gum for daily use for 6 weeks.
Reference Therapy	NA. There is no placebo. This is an effectiveness study using an over the counter drug.
Key Procedures	NA

Statistical Analysis	The primary analytic approach used to compare study arms is conditional logistic regression. This fixed effects approach was chosen as primary because of the modest number of sites and the fact that they are not very heterogeneous. Because some methodologists have advocated mixed effects models even when the number of sites is small, we will use a multilevel logistic regression model as an alternative, sensitivity analysis approach. In an intent-to-treat analysis of all study entrants, conditional logistic regression analysis will compare study arms on the primary outcome, 7-day point prevalence CO confirmed (<10 ppm) tobacco abstinence captured at 6-month follow up. The outcome will be regressed on indicator variables for study arm and OPC site will be the stratification variable. Pairwise comparisons of arms will be undertaken to determine which arms are significantly different. Pairwise comparisons will be adjusted for multiple comparisons using the Tukey method. Effect magnitudes will be based on odds ratios for the pairwise comparisons, which will be calculated by exponentiating the coefficients for pairwise contrasts. Secondary cessation outcomes, HIV-related outcomes, hypothesized mediators (e.g., risk perceptions, self-efficacy), and the food insecurity outcomes also will be analyzed with conditional logistic regression, or a different fixed effects regression appropriate to the type of outcome variable.
----------------------	---

SCHEMATIC OF DESIGN. This research has three phases. For Aim 1 we will conduct a formative

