4.2 STUDY ENDPOINTS
4.2.1 Primary. The primary endpoint is carbon monoxide confirmed smoking abstinence at 6 months.

4.2.2 Secondary. The secondary patient outcomes are self reported smoking cessation and reduction in number of cigarettes per day, and hypothesized mediators of the main outcome (risk perception, attitudes, norms and self-efficacy) at 3 and 6 months.

5. STUDY ENROLLMENT AND WITHDRAWAL.

5.1 INCLUSION CRITERIA.

5.1.2. Study site eligibility. We will recruit 13 OPCs from one city, Hanoi. The sites are very homogeneous in terms of staffing and infrastructure. Therefore, site eligibility will be based solely on the number of active patients to ensure adequate recruitment (>240 patients) and at least 4 providers per site. The CDC of Hanoi will assist with site recruitment.

5.1.3. Patient inclusion criteria. For Aim 1-3 men and women who are ≥ 18 , patients in the HIV OPCs, current tobacco users, live in Hanoi and reachable by phone are eligible. All patients of the OPCs are HIV+. We expect fewer women to be enrolled in all phases of this research because about 10-20% of patients in the OPCs are female, and their smoking prevalence is low (<2%). There are no enrollment restrictions based upon race and ethnicity. For the supplement we will enroll men and women who are >18 and patients in the HIV OPCs who are not current tobacco users.

5.1.4. Health care providers and staff inclusion criteria. All providers and staff currently working at the OPC will be eligible.

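### The 80% power stated for the 6-month cessation contrast on food insecurity is that of an unstratified t-test; under the fixed effects analysis by clinic that the plan writes, 75 smokers give about 72–76%

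*Combined protocol and SAP*

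**What the plan says.** Section 9.1, AIM 4, gives the power for the effect of quitting on the HFIAS score: "When estimating the impact of smoking cessation on HFIAS at the 6-month follow-up, power is 80% to detect a standardized mean difference of" 0.89, "given the proposed sample size of $n=75$ smokers at baseline" and "assuming at least 16% of smokers ($n=12$) achieve cessation". It names no test, no alpha and no adjustment for clinic.

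The analysis model appears elsewhere. The Protocol Summary (Statistical Analysis) says that secondary outcomes, mediators "and the food insecurity outcomes also will be analyzed with conditional logistic regression, or a different fixed effects regression" suited to the outcome type. Earlier in the same entry, for the primary outcome, "OPC site will be the stratification variable". The parallel list of outcomes in Section 9.1, AIM 2, leaves food insecurity out, so the Summary is the only place that assigns it a model. In both places multilevel regression is a sensitivity analysis.

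On differences between clinics, Section 5.1.2 says: "The sites are very homogeneous in terms of staffing and infrastructure". Section 9.1, AIM 2, gives low heterogeneity as one reason for making fixed effects primary.

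On the sample, the Schematic of Design and Section 9.1 have 75 smokers and 75 non-smokers. Section 4.1, AIM 4, has food insecurity data from 672 smokers at baseline and 6 months.

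**The concern.** A regression with a term for each clinic compares quitters with continuing smokers within clinics only. With 75 smokers in 13 clinics there are five or six per clinic, and 12 quitters will not fall evenly among them. Some clinics will have none and add nothing to the contrast; others will have several. A power figure that ignores clinic belongs to a different test.

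The third objective of the supplement, the effect of reduced tobacco use and cessation on food insecurity at 6 months, rests partly on this contrast. If the 75-smoker sizing is the real one, a null result would be read against more power than the written analysis has.

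**Working it through.** **Inputs from the documents.** Smokers 75, quitters 12, d = 0.89 (Section 9.1, AIM 4); 13 clinics (Protocol Summary).

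**Assumptions.** Two-sided alpha of 0.05, which the plan does not state for Aim 4; it reproduces the printed 80%, whereas one-sided 0.05 gives 87.6%. Smokers are spread as evenly as possible (ten clinics of 6, three of 5). Quitters fall at random over clinics. There are no covariates and no loss to follow-up. The plan gives no ICC, so a range is shown.

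**1. The plan's own figure.** For an unstratified two-sample t-test:

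- information = 12 × 63 / 75 = 10.08
- noncentrality = 0.89 × √10.08 = 2.83, with 73 df
- power = 79.6%; d for 80% power = 0.894

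The printed 80% at 0.89 is therefore correct for that test.

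**2. With clinic fixed effects.** The information is the sum over clinics of m(n − m)/n, where n is smokers and m quitters in the clinic. Under random placement its expected value is 10.08 × (75 − 13)/(75 − 1) = 10.08 × 62/74 = 8.45; about 4.6 of the 13 clinics are expected to have no quitter.

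- noncentrality = 0.89 × √8.45 = 2.59, with 75 − 13 − 1 = 61 df
- power = 72.1% at the expected information; 72.0% averaged over random placements (middle 95% of placements 64% to 76%)
- direct least-squares simulation: 72.9%
- d for 80% power = 0.98

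**3. Where the loss comes from.** Dropping to 61 df while keeping information at 10.08 leaves 79.4%. One quitter in each of 12 clinics gives information 10 × 5/6 + 2 × 4/5 = 9.93 and power 78.8%. So neither the lost degrees of freedom nor an even spread of quitters explains the fall. Chance clumping of quitters in small clinics does.

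**4. Range over ICC.** With total SD held fixed, removing between-clinic variance scales d by 1/√(1 − ICC).

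| ICC (assumed) | Power at d = 0.89 | d for 80% power |
|---|---|---|
| 0 | 72% | 0.98 |
| 0.05 | 74% | 0.98 × √0.95 = 0.96 |
| 0.10 | 76% | 0.98 × √0.90 = 0.93 |
| 0.15 | 79% | 0.98 × √0.85 = 0.90 |
| 0.20 | 81% | 0.98 × √0.80 = 0.88 |

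**5. Number of contributing clinics.** At ICC 0, power is about 75% with 8 clinics, 77% with 5 and 79% with 3.

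**6. All 672 smokers.** With 16% quitting (108), power at d = 0.89 under clinic fixed effects exceeds 99.9%, and d for 80% power is about 0.30.

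**The case against.** Several points weigh against a firm figure.

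- **Sample.** Section 4.1 puts 672 smokers in the 6-month food insecurity data, and on that set there is no shortfall. This stands, and it affects power more than the clinic term does. It does not rescue the printed statement, which is tied to 75 smokers and 12 quitters.
- **Model.** Section 9.1 names no Aim 4 model, and the stratification sentence in the Summary is written for the primary outcome. Reading clinic as the fixed effect for HFIAS is an inference from the sentence that follows it, but no other model is offered.
- **Covariates.** Section 9.1, AIM 2, calls for patient covariates in all analyses. Three to five that explain nothing lower power to 70% and 68%; covariates explaining about 18% of residual variance restore 80%. Baseline HFIAS is collected, though adjustment for it is not written; an assumed correlation with the 6-month score of 0.4 would give about 79%, and 0.5 about 83%. Power is therefore not fixed at 72%.
- **Effect and quit rate.** The plan equates d = 0.89 with 6 points. At the SD of 6 given for the baseline comparison, 0.89 is 0.89 × 6 = 5.34 points and 6 points is d = 1.0, where fixed effects power is 81%. With 15 or 16 quitters it is 79% to 81% at 0.89. Both are departures from the stated design point, and either would raise the unstratified power too.

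A reader might also infer that the random-intercept model should become primary, since in simulation it kept 80% power at ICC 0, 0.05 and 0.10. The documents do not support that. They choose fixed effects deliberately, and quitting is not randomised, so within-clinic comparison guards against clinic-level confounding that a random intercept assumes away.

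**Conclusion.** The point holds in limited form. The stated 80% is correctly computed, but for a test other than the one the plan writes. With 75 smokers over 13 clinics, 12 quitters placed at random, two-sided 0.05 and no covariates, the written analysis has about 72% power at d = 0.89 at ICC 0, 74% at 0.05 and 76% at 0.10. The low end fits the plan's own view that clinics differ little. Fewer contributing clinics, useful covariates or a larger ICC would narrow or close the gap; uninformative covariates would widen it.

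A reader might conclude that the objective is underpowered and that a true effect of this size would be missed 28% of the time. That goes too far: it takes one set of unstated inputs as fact and ignores the 672 smokers in Section 4.1. What the documents do show is a power statement that does not match its analysis, and a sample that is stated in two ways.

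**What to change.** 1. In Section 9.1, AIM 4, write the model for the 6-month contrast (regression of HFIAS on cessation with site fixed effects as primary, multilevel regression as sensitivity, as in the Protocol Summary), together with the alpha and any covariates.
2. Reconcile the 75 smokers in the Schematic and Section 9.1 with the 672 in Section 4.1.
3. If 75 is right, restate the power: about 72–76% at d = 0.89 for ICC 0–0.10 before covariates, with 80% reached at d of about 0.96–0.98 for ICC 0–0.05. If all 672 are analysed, recompute on that set.
4. While editing the sentence, make the 6-point difference, the SD and d agree.

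The cost is a few sentences, with no new patients or data. If 75 stays, the printed power becomes somewhat less favourable.
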